**AUGMENTED MEDIAL RECTUS MUSCLE RECESSION VERSUS MEDIAL RECTUS
RECESSION WITH POSTERIOR SCLERAL FIXATION IN PARTIALLY
ACCOMMODATIVE ESOTROPIA**

FULL PROTOCOL

Principal investigator(s):

[name], MD, Professor of Ophthalmology, Cairo University

[name], Professor of Ophthalmology, Cairo University

Clinical Trials Registration Number: NCT02413463

Submitted to Cairo University Ophthalmology Department Medical Research Approval Committee on December 10th, 2014

Final revision approved on January 10th, 2015

INTRODUCTION:

The initial treatment of partially accommodative esotropia (PAET) is correction of the full hyperopic error. Surgery is needed if there is residual esotropia \geq 12 prism diopters for distance and near, and/or if the patient is not attaining fusion ¹. A variety of surgical approaches have been proposed to decide the surgical target angle on which the amount of muscle surgery is based. These strategies include: the standard formula ², prism adaptation ³, and the enhanced ⁴ and the augmented surgical formulas ⁵.

However overcorrection might occur with augmented recession, and often requires reduction of hyperopic correction to maintain alignment. Such overcorrection might carry the risk of development of consecutive exotropia later on ^{6,7}.

Various methods have been described before to address variability in the angle of the deviation in esotropia including posterior scleral fixation ⁸, pulley fixation ⁹, slanting recession ¹⁰, combined recession-resection ¹¹ and Y-splitting of the medial rectus muscle ¹². While these modalities have been described before in the management of convergence excess esotropia because of their ability to reduce the variability in the angle especially for near, their value in PAET have not been adequately studied.

The aim of this study is to evaluate whether posterior scleral fixation sutures can adequately address the variability of the angle of deviation in children with PAET while minimizing the risk of postoperative overcorrection.

METHODS:

A prospective controlled interventional study will be performed on patients with partially accommodative esotropia. An informed consent for the surgery will be obtained from all patients. All patients' guardians will receive a thorough explanation of the study design and aims, and signed a written informed consent.

All patients will receive a full ophthalmological assessment including history taking, measurement of uncorrected and best-corrected visual acuity, cycloplegic refraction, anterior segment examination, as well as a dilated fundus examination.

In addition, all patients will have a detailed motor examination during the initial evaluation and at each follow-up period. The angle of misalignment will be measured by the prism and alternating cover tests for both distance and near with and without glasses. The angle of horizontal misalignment will also be measured in side gazes and in straight up and down gazes. Measurement of the angle of deviation in up and down gazes will be done by tilting the head, approximately 25 degrees down and up respectively, with the patient fixing on a distance target. The difference between the angles of horizontal misalignment in up and down gazes will be used to calculate the amount of pattern strabismus if present.

The ductions and versions in all cardinal directions of gaze will be analyzed before surgery and thereafter during the postoperative follow up visits. Underaction will be measured on a 4-point

scale ranging from -1 to -4. Similarly overaction will be measured on a 4-point scale ranging from +1 to +4.

In all patients cycloplegic refraction will be performed using cyclopentolate 1% eye drops instilled 3 times 10 minutes apart with the last time 30 minutes before refraction. Patients with hypermetropia with a spherical equivalent $\geq +1.5$ D will then be prescribed the full cycloplegic refraction and then re-evaluated with spectacles one month later. Patients who appear to have a partially accommodative esotropia defined as residual esotropia >8 PD for distance with spectacles will have repeat refraction using atropine 1% drops 3 times a day for 3 days before refraction.

After ensuring that full cycloplegic refraction was prescribed, patients will then be evaluated with glasses to identify those with partially accommodative esotropia without convergence excess. Patients will be included in the study if the residual distance angle with cycloplegic prescription was > 15 PD. Patients with convergence excess esotropia, defined as the angle of deviation with glasses for near exceeding that for distance by 15 PD or more will be excluded from the study.

Amblyopia will be defined as a difference of 0.3 logMAR in verbal children (3 lines on the standard logMAR visual acuity chart) or a strong unilateral fixation preference using an accommodative target in infants and preverbal children. All patients with amblyopia will be treated before surgery. In general amblyopia therapy was continued till there was no further improvement of visual acuity or fixation preference despite adequate compliance with therapy for an acceptable

duration. Amblyopia will be treated following the standard clinical practice using part-time occlusion and in concordance with the PEDIG guidelines ¹³. Anisometropia is defined as a difference in the spherical equivalent of both eyes by 1 D or more.

Patients with neurologic, ocular, or developmental disorders or follow-up less than 6 months will be excluded from the study. In addition, patients will be excluded if they showed oblique muscle dysfunction, vertical deviation, significant A or V patterns, paralytic or restrictive forms of strabismus, or had a history of prior eye muscle surgery.

The smallest angle of deviation is defined as the corrected angle for distance. The largest angle is defined as the angle for near measured without correction. The angle disparity is defined as the difference between the largest and smallest angles.

Patients will be randomly allocated using a random table to one of two groups. In one group bilateral augmented MR muscle recession will be performed (augmented group). In the other group bilateral MR muscle recession combined with posterior scleral fixation sutures will be performed (Faden group).

The surgeries will be performed by one of two surgeons ([name]) using the same surgical technique. In both groups the medial rectus muscle will be exposed and hooked through a limbal approach. The muscle will then secured with 6-0 polyglactin (Vicryl, Ethicon, Somerville, NJ) sutures.

In the augmented group, the medial rectus muscles will be recessed using standard tables ¹⁴ with the surgical dose targeting the average of the largest and smallest angles.

In the Faden group, medial rectus muscle recession will be performed as described above with the surgical dose targeting the smallest pre-operative angle. The muscle will then fixated to the sclera using 6/0 polyester sutures placed in a mattress like with the anterior and the posterior sutures passing through both the edge of muscle and the sclera 12 mm and 14 mm from the muscle insertion, respectively.

Patients will be followed up at 1 week, 1 month, 3 months and 6 months after surgery. The distance and near angles of deviation, with and without glasses, and the angle disparity will be measured at each follow up visit and the ductions and versions were assessed in all patients.

Patients will be considered to have successful outcome if both the distance and near angles with spectacles were less than 8 PD esotropia/phoria. Patients who develop any exophoria/tropia, or in whom hyperopic correction needed to be reduced for treatment of a consecutive exotropia will be considered to be unsuccessful ^{6, 7, 15}. In addition, patients will be further subdivided into 2 groups according to the preoperative angle disparity into those with angle disparity 20 PD or less and those with angle disparity more than 20 PD. The success rate in each subgroup will be calculated.

For categorical variables (e.g., gender), percent distribution will be used. For continuous variables (e.g. age, angle of deviation), mean, range and standard deviation were used. Comparisons between the two groups will be done using t-test for independent samples for continuous variables

and chi square test for categorical variables. Statistical analysis will be performed with SPSS for Windows (SPSS Inc., Chicago, IL).

SAMPLE SIZE:

An estimation of sample size was performed considering a study power of 0.8 with an alpha error of 0.05 aiming to detect a difference of 5 Δ in the postoperative angle disparity between the 2 groups, assuming a postoperative standard deviation of 6 Δ⁹. Based on this estimation, a total of 24 eyes were found to be adequate in each group, and considering a 25% dropout during the follow-up, recruitment of 30 study subjects in each group will be targeted

EXPECTED START DATE: 1 January 2015

EXPECTED COMPLETION DATE: 31 December 2016

REFERENCES:

1. von Noorden G. Binocular vision and ocular motility (5th ed), St. Louis: Mosby. 1996: 307-308.
2. Parks M.. Concomitant esodeviations. In: Parks M.. Ocular Motility and Strabismus, Hagerstown: Harper & Row 1975: 99-111.

3. Prism Adaptation Study Research Group. (1990). Efficacy of prism adaptation in the surgical management of acquired esotropia. *Arch Ophthalmol* 1990; 108: 1248-55.

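### Excluding patients with under 6 months of follow-up acts after randomisation and surgery, gives a completers-only comparison, and can drop known failures

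*Combined protocol and SAP*

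**What the plan says.** The combined protocol and SAP gives the exclusion in METHODS, in the same sentence as baseline conditions: "Patients with neurologic, ocular, or developmental disorders or follow-up less than 6 months will be excluded from the study".

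The design is randomised: "Patients will be randomly allocated using a random table to one of two groups". Both groups are defined by the operation performed. Follow-up is described only in relation to that operation: "Patients will be followed up at 1 week, 1 month, 3 months and 6 months after surgery". Outcome data accrue throughout: "The distance and near angles of deviation, with and without glasses, and the angle disparity will be measured at each follow up visit".

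The failure rule, later in METHODS, names no visit or time window. It classes the following as failures: "Patients who develop any exophoria/tropia, or in whom hyperopic correction needed to be reduced for treatment of a consecutive exotropia".

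SAMPLE SIZE expects losses: "considering a 25% dropout during the follow-up, recruitment of 30 study subjects in each group will be targeted". The analysis text in METHODS names an independent-samples t-test and a chi-square test. It does not say which patients enter them or what is done when the 6-month visit is missing.

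**The concern.** An eligibility criterion should be decidable before allocation. This one cannot be, because the length of post-surgical follow-up is known only afterwards. Applied literally, it removes randomised and treated patients according to something that happened after treatment, so the groups compared are no longer the groups that were randomised. If leaving is related to outcome, and differently so in the two arms, both the disparity and the success contrasts are biased.

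The arms may well differ in the event that defines early failure. The INTRODUCTION says of one of the two procedures: "However overcorrection might occur with augmented recession, and often requires reduction of hyperopic correction to maintain alignment". Limiting postoperative overcorrection is part of the stated aim. A rule that can discard patients who have already overcorrected therefore touches the event the trial is meant to compare. The documents do not, however, link overcorrection to dropout.

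**Working it through.** **1. Can the two rules be reconciled?** Take a patient who develops an exodeviation at the 1-month visit and does not return after 3 months.

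- Failure definition: unsuccessful, because no time limit is given.
- Exclusion criterion: out of the study, because follow-up is under 6 months and no exception is made.

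Nothing says which rule prevails, so the success denominator is undefined for such patients. Their disparity values at 1 week, 1 month and 3 months exist, but the plan does not say whether they are used.

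**2. The plan's own figures.** Inputs from SAMPLE SIZE: difference 5 PD, SD 6 PD, alpha 0.05 (two-sided taken), power 0.80, 24 per group, 30 recruited, 25% dropout.

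- A t-test with standardised difference 5/6 needs 23.6, rounded up to 24 per group. The stated 24 is reproduced.
- 24 × 1.25 = 30, the stated target.
- Going from 30 to 24 is a loss of 6/30 = 20%; 25% of 30 is 7.5. Planned loss is therefore 6 to 8 per arm. This is a planning figure, not a cap.

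**3. Success: limits that need no assumption about why patients leave.** Let s1 and s2 be the observed successes and m the number missing in each arm of 30. The full-group difference lies within ±m/30 of (s1 − s2)/30.

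| m | limit |
|---|---|
| 6 | ±6/30 = ±20 points |
| 7 | ±7/30 = ±23 points |
| 8 | ±8/30 = ±27 points |

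Counting failures already seen before patients left would narrow these limits.

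**4. Success: an illustration under a strong assumption.** Suppose true success is 21/30 in both arms, so there is no real difference.

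- 7 lost per arm. One arm loses 5 failures and 2 successes: 19/23 = 83%. The other loses 2 failures and 5 successes, about what non-informative loss gives: 16/23 = 70%. The spurious gap is 13 points; uncorrected chi-square 1.08, p = 0.30. In the first arm failures leave (5/9)/(2/21) = 5.8 times as often as successes.
- 6 lost per arm, with 4 and 2 failures among them: 19/24 against 17/24, a gap of 8 points (p = 0.50).

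**5. Disparity: an illustration.** Let f be the fraction of one arm excluded and d the mean of the excluded minus the mean of those kept. The completer mean differs from the full-arm mean by −f × d. Loss in the other arm is taken as non-informative. The range of 3 to 10 PD for d is an assumption.

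- Low end: 0.20 × 3 = 0.6 PD.
- High end: 0.25 × 10 = 2.5 PD, half of the 5 PD target.

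Two-sided t-test, noncentral t, SD 6 PD among completers:

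| Shift | n per arm | False-positive rate | Power if the shift opposes a true 5 PD effect |
|---|---|---|---|
| none | 22–24 | 5% | 77–81% (no opposing shift) |
| 0.6 PD | 24 | 6.3% | 70% (net 4.4 PD) |
| 2.5 PD | 22–23 | 27–28% | 27–28% (net 2.5 PD) |

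The two entries in the last row coincide because the net effect is 2.5 PD in both cases.

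**The case against.** The case on the other side has five parts.

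- **Intent.** The phrase may be a loosely worded requirement that patients be available for 6 months, since it sits among baseline conditions. The text does not say so, and follow-up is scheduled only after surgery. Even on that reading the wording needs correcting, and no missing-data rule is supplied.
- **Harm is conditional.** Bias in the contrast needs loss that depends on outcome and differs between arms. This stands. The success illustration requires a strong departure from random loss, and even then is far from significant.
- **The upper disparity figure is extreme.** A 10 PD gap is 10/6 = 1.67 SDs. With 25% excluded it adds 0.25 × 0.75 × 10² = 18.75 to a variance of 36, so an SD of 6 among completers means about 7.4 in the whole arm. That does not invalidate the calculation, because the t-test sees only the completers' SD. It does show how far out this end lies. A gap of 3 to 6 PD gives a shift of 0.6 to 1.5 PD and a false-positive rate of about 6% to 13%.
- **The ±20 to ±27 points are not specific to this wording.** Any trial with this much missing outcome would have them. This is correct: the exclusion itself adds the discarding of observed failures and earlier visits, and the documents do not allow that part to be quantified.
- **The remedy could overreach.** A mixed model and multiple imputation are not the only acceptable methods with 30 per arm. They are offered below as examples.

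**Conclusion.** The concern holds and must be fixed. As written, the plan removes randomised and treated patients on a post-treatment criterion, and it contradicts its own failure definition for anyone who fails early and then leaves. This is an instruction that produces the wrong analysis set if followed, not merely a missing detail. That conclusion rests on the text and on the principle of keeping the randomised groups intact; it does not depend on the illustrations.

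On size, the only assumption-free statement is the ±20 to ±27 point limit for success with 6 to 8 missing per arm. The disparity shift of 0.6 to 2.5 PD rests on the assumed 3 to 10 PD gap, with the upper end extreme. Neither the magnitude nor the direction of any actual bias can be obtained from the documents.

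**What to change.** In METHODS, delete the 6-month follow-up phrase from the exclusion criteria and state that every randomised patient is analysed in the allocated group. Then add the following.

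- **Disparity:** use all scheduled visits, for example in a repeated-measures mixed model with the 6-month between-group contrast as the estimate. METHODS names no assessment visit, so that time point should be stated openly as a choice.
- **Success:** apply the existing failure rule at any attended visit, identically for completers and leavers, so an exodeviation or a reduced correction for consecutive exotropia counts as failure whenever it occurs. The present wording supports this reading but gives no window, so the window should be written down.
- **Leavers who had not failed:** keep them in the denominator under one pre-stated method, for example multiple imputation from earlier angles and arm, with best-case and worst-case sensitivity analyses.
- **Reporting:** give losses by arm with reasons, and keep the 6-month completer analysis as secondary.

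The cost is protocol and analysis wording plus a little more analysis work. No visits or measurements are added, since angles and disparity are already recorded at each visit. If all 30 per arm have usable outcomes, power for 5 PD is about 89%, against 77–79% with 22–23 completers; imputing missing outcomes would recover only part of that. The downsides are a missing-at-random assumption for leavers who had not failed, and success rates that may look slightly less favourable.

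### Preoperative angle disparity, the baseline of the sample-size endpoint, is neither balanced by the described allocation nor adjusted for in the analysis, so precision is lost

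*Combined protocol and SAP*

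**What the plan says.** Allocation takes one sentence in Methods: "Patients will be randomly allocated using a random table to one of two groups". No sequence type, block size, stratification factor or minimisation is described there or elsewhere.

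Methods defines angle disparity as the largest angle (near, uncorrected) minus the smallest (distance, corrected). Both angles are measured in all patients at the initial evaluation. The augmented arm's surgical dose targets the mean of those two angles, and the Faden arm's targets the smallest.

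For the outcome, "patients will be further subdivided into 2 groups according to the preoperative angle disparity". The cut is at 20 PD, and a child at exactly 20 PD falls in the lower group. The plan for these groups is brief: "The success rate in each subgroup will be calculated". Group comparisons use the independent-samples t-test for continuous variables and the chi-square test for categorical ones. No covariate is mentioned.

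Sample Size is based on postoperative angle disparity, "aiming to detect a difference of 5 Δ in the postoperative angle disparity between the 2 groups". Power is set at 0.80 and alpha at 0.05, and the SD of that endpoint is taken as 6 PD. After an allowance for 25% dropout, "recruitment of 30 study subjects in each group will be targeted".

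**The concern.** Preoperative disparity has the strongest claim of any baseline variable here to be balanced or adjusted for.

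- It is the baseline value of the only endpoint used to size the trial.
- It enters the treatment contrast. The mean of the largest and smallest angles equals the smallest plus half the disparity, so the two arms' target angles differ by half of each child's disparity.
- The plan itself treats it as prognostic by splitting the success rate on it.

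Nothing described in the allocation limits how unevenly large-disparity children may fall between the arms, and nothing in the analysis corrects for it. At stake is the precision of the main comparison in a trial of 60 children, together with the balance of the four subgroup-by-arm cells.

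**Working it through.** **Inputs from the documents.** Difference 5 PD, SD 6 PD, alpha 0.05, power 0.80, 30 per group, 25% dropout, split at 20 PD. Two-sided testing is assumed, since sidedness is not stated.

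**Inputs not in the documents (assumed).** Size of each disparity subgroup; correlation r between preoperative and postoperative disparity; success rates of 60% and 80% for the subgroup check.

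**1. The plan's own sample size.** The normal approximation gives n = 2 × [6 × (1.960 + 0.842) / 5]² = 22.6, so 23 per group. The exact t-test uses noncentrality (5/6) / √(1/n₁ + 1/n₂) on n₁ + n₂ − 2 degrees of freedom. It gives power 0.789 at 23 per group and 0.807 at 24, so the stated 24 is reproduced. Then 24 × 1.25 = 30. With 25% lost, 30 × 0.75 = 22.5 per group, or about 45 children (22:23), and power is 0.780.

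**2. Arm sizes, if allocation is simple.** The number in one arm is Binomial(60, 0.5).

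| Split | Probability of this or worse | t-test power, all 60 analysed |
|---|---|---|
| 30:30 | – | 0.888 |
| 24:36 | 0.155 | 0.875 |
| 22:38 | 0.052 | 0.864 |

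Averaged over simple randomisation, power is 0.882. Arm-size imbalance costs about half a point on average.

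**3. Balance of disparity, if 30 of 60 exceed 20 PD.**

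- Fixed 30:30 arms: a gap of 20 points means 18 of 30 against 12 of 30. The hypergeometric probability of that or worse is 2 × 0.098 = 0.196.
- Simple randomisation: the hypergeometric probability averaged over the binomial arm sizes is 0.155.

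With 20 of 60 in one subgroup, the corresponding figures are 0.17 (fixed arms) and 0.12 (simple). With 15 of 60 they are 0.07 and 0.09.

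**4. Gain from adjustment.** The residual SD is 6 × √(1 − r²), taking 6 as the unadjusted SD. With 22:23 analysed, √(1/22 + 1/23) = 0.298, and one further degree of freedom goes to the covariate (42 left).

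| r (assumed) | Residual SD | Noncentrality | Power |
|---|---|---|---|
| 0 (t-test, 43 df) | 6.00 | 2.79 | 0.78 |
| 0.3 | 5.72 | 2.93 | 0.82 |
| 0.5 | 5.20 | 3.23 | 0.88 |

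**5. Subgroup cells.** For assumed success rates of 60% and 80%, power within a subgroup is 0.22 at 15 per cell and 0.16 at 10 per cell, even with perfect balance.

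**6. Effect of stratified blocks.** With blocks of 4 in two strata, each stratum can be off by at most 2. The worst arm split is 32:28, with power 0.886.

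**The case against.** The best defence is that allocation from a random table, stratified or not, is valid. The t-test's type I error holds on average over randomisations, and with all 60 children analysed the unadjusted power is already 0.888. All of that stands, and it limits the point to precision. It does not remove the case for adjustment, because after the plan's own 25% dropout the unadjusted power falls to 0.78, below the 0.80 sought.

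A reader might infer four stronger things that the documents do not support.

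- **That allocation is unrestricted.** The plan does not say so. A target of 30 in each group is compatible with a list constrained to equal arms. The supportable statement is that no restriction is described.
- **That the arms could be damagingly unequal.** A 24:36 split costs 0.013 of power.
- **That imbalance biases the result.** If postoperative disparity differed by 5 PD between the subgroups (assumed), a 20-point imbalance would move the unadjusted difference by 0.20 × 5 = 1 PD. The standard error at 30:30 is 6 × √(2/30) = 1.55 PD, so this is chance error within one standard error. If the SD of 6 describes all children, it already includes the spread between subgroups.
- **That stratifying would make the subgroup results informative.** It would not, as the power at 15 per cell shows. The plan also only calculates those rates and makes no claim to test them. Balance at allocation need not survive dropout either.

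**Conclusion.** The point holds as one of efficiency. A strong candidate covariate is available before surgery at no extra cost, and the plan uses it neither in the described allocation nor in the comparison of groups. A gap of 20 points or more in the share above 20 PD has a probability of about 0.16 (simple randomisation) or 0.20 (fixed 30:30 arms), provided half the children exceed 20 PD. The plan does not give that proportion, and a more uneven split changes the figures. Adjustment is worth about 4 to 10 points of power with some 45 children analysed, for an assumed correlation of 0.3 to 0.5 and an unadjusted SD of 6. A weaker correlation would bring less. The trial is valid without the change, so this is a desirable improvement and not a critical defect.

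**What to change.** **Analysis (main change).** Replace the unadjusted t-test on postoperative angle disparity with a linear model (ANCOVA) containing treatment group and continuous preoperative disparity. Adjust the comparison of success rates for the 20-PD stratum, for example with a Mantel-Haenszel analysis over the two strata. This needs no new data and costs one degree of freedom in the linear model.

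**Allocation (if the list can still be set).** State the sequence type, and use 1:1 permuted blocks stratified by preoperative disparity (20 PD or less, more than 20 PD). Two strata are workable with 60 children. The cost is a new list, a protocol sentence and slightly more administration, since disparity must be on record before each assignment.

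**Reporting.** Label the success rates by disparity subgroup as descriptive, because the cells are small even when balanced.

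### Two surgeons share the cases, but the surgeon is not fixed before allocation, balanced across arms or included in the analysis; this costs some precision, and causes bias only if surgeon choice follows the arm

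*Combined protocol and SAP*

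**What the plan says.** The METHODS paragraph on allocation reads "Patients will be randomly allocated using a random table to one of two groups". It describes no stratification, blocking or concealment. The next paragraph states "The surgeries will be performed by one of two surgeons", followed by "using the same surgical technique", and then sets out the approach, suture material, dosing table and fixation points. No sentence says who decides which surgeon operates on which child, or whether that is decided before the arm is known.

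The last METHODS paragraph gives the analysis: "Comparisons between the two groups will be done using t-test for independent samples for continuous variables", with a "chi square test for categorical variables". The only planned split of the patients is by preoperative angle disparity. Surgeon does not appear in the analysis.

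The SAMPLE SIZE section gives the yardstick: "aiming to detect a difference of 5 Δ in the postoperative angle disparity between the 2 groups", "assuming a postoperative standard deviation of 6 Δ".

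**The concern.** Randomisation protects a comparison against factors that are settled before the arm is drawn. The operating surgeon need not be settled by then. Under this text a child could be allocated first and given a surgeon second, and the two operations are not technically identical, because the Faden arm adds scleral fixation. A preference for, or greater familiarity with, one operation could therefore steer cases. If it did, part of any difference between the surgeons would be counted as a difference between the operations, and the planned tests have no means of removing it. Even without steering, variation between surgeons stays in the error term of a trial planned at about 80% power.

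**Working it through.** **Inputs from SAMPLE SIZE.** Difference 5 PD, SD 6 PD, power 0.8, alpha 0.05, 24 evaluable per group, 30 recruited per group.

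**Assumptions, not in the documents.** Two-sided test; 24 evaluable children per arm (the protocol writes eyes); 6 PD taken as the SD within surgeon; equal caseloads overall; a surgeon difference g in mean postoperative disparity of 2, 3 or 5 PD.

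**1. The plan's own figure.** The normal formula gives 2 × (1.960 + 0.842)² × 36 / 25 = 22.6, so 23. The t-distribution version gives 23.6, so 24, with power 0.807. The stated 24 reproduces.

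**2. Surgeon unrelated to arm.**
- The SD within an arm becomes √(36 + g²/4), which is 6.08, 6.18 or 6.50 PD for g = 2, 3 or 5.
- Power for 5 PD becomes 0.80, 0.78 or 0.74, against 0.81 with no surgeon difference.
- Simulated type I error of the unadjusted t-test is 0.049 to 0.051 in all three cases.
- With 30 children per surgeon and 30 per arm, the gap between arms in one surgeon's share has an SD of 13 points. A gap of 25 points or more has probability about 7%; a gap of 60 points or more, about 6 in a million.

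**3. Surgeon choice follows the arm.** Let one surgeon's share be p in one arm and 1 − p in the other.
- Bias = g × (2p − 1).
- SD within an arm = √(36 + g² p(1 − p)).
- The false-positive rate is the chance that the t-test with 24 per arm rejects at that bias when the operations do not differ.

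| Share in the two arms | Bias for g = 2, 3, 5 PD | False-positive rate |
|---|---|---|
| 70/30 v 30/70 | 0.8, 1.2, 2.0 PD | 7%, 10%, 18% |
| 80/20 v 20/80 | 1.2, 1.8, 3.0 PD | 10%, 17%, 36% |
| one surgeon per operation | 2, 3, 5 PD | 20%, 40%, 81% |

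For example, at 70/30 and g = 5: bias = 5 × 0.4 = 2.0 PD, and SD = √(36 + 25 × 0.21) = 6.42 PD.

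**4. With a surgeon term in a linear model.** The standard error of the treatment difference is 6 × √(2/24) / √(1 − gap²).
- Gap 0: 1.73 PD, power 0.81.
- Gap 0.4: 1.89 PD, power 0.74.
- Gap 0.6: 2.17 PD, power 0.62.
- Gap 1: the divisor is zero, so the two effects cannot be estimated apart.

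Simulation with the realised gap left to vary gives power of about 0.80 with equal shares and 0.72 at 70/30. Type I error is 0.049 to 0.052 throughout (g = 3 or 5).

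**The case against.** The protocol does more than name two surgeons. It requires a common technique and specifies the approach, sutures, dosing table and fixation points, which should keep a surgeon difference small. An assumed difference of 5 PD equals the whole planned effect and is 0.83 SD, so it is an extreme upper end. Disparity is also a difference between two angles in the same child, so a surgeon who shifts both angles equally would move it little. All of this stands, and it argues for the lower part of the range. It does not dispose of the point: a shared technique does not decide who operates in which arm, and the success outcome depends on each corrected angle separately, so a uniform shift would not cancel there.

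Three stronger readings are tempting, and the documents support none of them.
- A reader might infer that surgeons were assigned by operation. The text is silent; it supports only the statement that this is not prevented.
- A reader might infer that chance imbalance between surgeons inflates the false-positive rate. A raised rate applies only conditionally on a large gap having occurred. Averaged over allocations the rate is nominal, as step 2 shows.
- A reader might infer that surgeon and operation could never be disentangled. That is so only if each surgeon does one operation; with overlap, and surgeon recorded, a model separates them at some cost in power.

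Nor do the documents say who measures the angles, so a difference in measuring habits between the surgeons cannot be relied on as a mechanism.

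**Conclusion.** The gap is real and moderate. The plan leaves surgeon choice open after allocation, does not balance it and does not adjust for it. If surgeon is unrelated to arm, the loss is 1 to 7 points of power and no inflation of type I error. If surgeon choice follows the arm, the unadjusted comparison is biased: at 70/30 versus 30/70, by 0.8 to 2.0 PD against a 5 PD target. These sizes rest on surgeon differences of 2 to 5 PD, which are assumed, and the documents give no basis for judging how likely arm-dependent assignment is. The stated sample size is not in dispute here. The change is worth making because it is cheap and removes the systematic route to bias at its source; later adjustment loses power as the gap grows.

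**What to change.** **METHODS, allocation and surgery.** Record the operating surgeon for each child before the allocation is revealed. Stratify the allocation list by surgeon, with randomly varying block sizes, and have someone other than the surgeons hold it concealed. The last two safeguards matter: the surgeons cannot be masked to the operation, so with a fixed block size each could follow their own list and guess the next allocation.

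**METHODS, statistical analysis.** Compare postoperative disparity with a linear model containing arm and surgeon. Compare success with a Mantel-Haenszel test stratified by surgeon. Report the number of children by surgeon and arm.

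**Cost.** A second list, someone to hold the lists, and one degree of freedom; no extra patients. The surgeon named beforehand is expected to do the case. Exceptions should be recorded, and those children analysed under the surgeon named beforehand.
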